- b. Unable to be contacted: 16 intervention participants were randomized but were not able to be contacted by POH to start the intervention and were considered as early withdrawals. Control participants could not be excluded as "early withdrawals" because the next visit would be a month after the baseline. Therefore, researchers modified the protocol and made a phone call to the control participants, right after the randomization, to simulate the call that the intervention participants had by POH to be enrolled in the food and nutrition program. From among control participants called right after randomization in the modified protocol, 2 could not be reached and were considered early withdrawals.

The number of participants with major and minor protocol deviations will be summarized by study arm.

16) Analysis populations – definition of analysis populations, e.g. intention to treat, per protocol, complete case, safety

- a. Intent to treat - The primary analysis will be intent to treat (ITT). The ITT analysis will include all participants in both arms who were randomized, completed all baseline assessments, and who had at least one follow-up visit. (see CONSORT).
- b. Adjusted intention to treat analysis. To adjust for early withdrawals, a propensity score for receiving the intervention will be developed and used to estimate the probability of each participant to receive the intervention. The adjusted ITT analysis will be performed adjusting for the propensity score and for baseline covariates that were different between arms.
- c. Per protocol - The per protocol analysis will include all participants in the ITT sample with baseline and follow-up evaluations and who adhered to the food and nutrition intervention. The minimal adherence will be considered as receiving at least 50% of weeks food and groceries, and at least 1 visit with the dietitian. This definition may be

revised depending on the distribution of adherence in the intervention participants. See appendix 1 for details about the food and nutrition education intervention.

- d. Complete case— We will not conduct complete case analyses as we will attempt to use all available data from all participants.

Section 5: Trial Population

17) Screening Data –

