Table 1: Baseline characteristics of CaRDS participants

Socio-demographic	Age, current gender, race/ethnicity, household size, relationship status, educational attainment
Economic welfare	Household food insecurity, sources of income, food support sources
Clinical	Heart failure quality of life; general health-related quality of life; medication inventory; blood pressure
Nutrition	Dietary quality; food consumption patterns
Mental Health	Depressive symptoms
Behavioral	Self-reported medication adherence; alcohol use, drug use
Healthcare utilization	Recent hospitalizations, ED visits, doctor visits

Section 6: Analysis

22) **Outcome definitions**

a. Aim 1: Primary Outcomes: Heart failure quality of life: The primary outcome for Aim 1 will be heart failure quality of life, which was assessed using the Kansas City Cardiomyopathy Questionnaire (KCCQ) at baseline, 1 month and 5 months, among all study participants. The Kansas City Cardiomyopathy Questionnaire is a 23-item instrument that quantifies physical function, symptoms (frequency, severity and recent change), social function, self-efficacy and knowledge, and quality of life. An overall summary score can be derived from the physical function, symptom (frequency and severity), social function and quality of life domains. A clinical summary score can be obtained from the symptom frequency and burden domains and the physical limitation domain. Scores are transformed to a range of 0-100, in which higher scores reflect better health status.

For analysis of the primary outcomes, we will compare:

- i. Change in the overall KCCQ scores from baseline to five months, by study arm.
- ii. Change in the overall KCCQ scores from baseline to one month, by study arm.
- iii. Change in the KCCQ clinical summary score from baseline to five months, by study arm,
- iv. Change in the KCCQ clinical summary score from baseline to one month, by study arm,
- v. Change in the overall physical domain KCCQ scores from baseline to five months, by study arm.
- vi. Change in the overall physical domain KCCQ scores from baseline to one month, by study arm.

b. Aim 1: Secondary outcomes:

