- a. **Preliminary/Descriptive analyses.** Frequency tables for all variables and measures of central tendency and variability for continuous variables will characterize the sample and be stratified by randomization arm to check for non-equivalence. If the two arms differ at baseline on any covariates, propensity scores approach will be used to obtain the desired marginal effect estimates under the counterfactual assumption of balanced arm.

25) Analysis methods to be used and how the treatment effects will be presented:

- a. Aim 1, Hypothesis 1. The intervention will lead to improved heart failure quality-of-life (primary outcome) and reduced acute care utilization (secondary outcomes) in the intervention arm compared to the control arm. Intent-to-treat analyses will assess whether the intervention will result in improved changes in primary and secondary outcomes with mixed effects models. These mixed models are equivalent to repeated measures models. Study arm (intervention or control), visits (baseline, month 1 and month 5), and the interactions between arms and visits will be the fixed effects and individuals will be considered as random effects.

Alternative analyses will be done using analysis of covariance in which the 5 month (and 1 month) outcome measures will be regressed on the corresponding baseline outcome measures and study arm. Analysis of covariance allows relaxing the assumption that the

baseline and follow-up measures have a 1:1 relationship and testing the assumption that the relationship between the baseline and follow-up measures are the same.

Additional analyses will be done to check robustness if the two arms differ at baseline by controlling for the propensity score or the covariates that were important in the propensity score.

For primary and secondary outcomes, Box-Cox transformations will be used to correct for skewness if needed.

To compare the probabilities of hospitalization and emergency room visits by study arm, a log-rank test will be performed, and visualized using Kaplan-Meier curves.

- b. Aim 2, Hypothesis, The intervention will improve food security, reduce healthcare utilization, and improve dietary behavior, that in turn will improve mental health (depressive symptoms), and medication adherence. Analysis for intermediate outcomes will be performed using mixed effects models, as described in Aim 1.
- c. Any planned sensitivity analyses for each outcome, where applicable: Not applicable.

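### Read most directly, the plan adds the propensity score to the mixed model without a visit interaction, where it can barely change the estimated difference in KCCQ change

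*Combined protocol and SAP*

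**What the plan says.** Item 25a (Section 6, Aim 1) sets out a mixed model with arm, visit (baseline, month 1, month 5) and their product: "the interactions between arms and visits will be the fixed effects and individuals will be considered as random effects". Baseline KCCQ is thus an outcome row, and the effect is the between-arm difference in change. The first comparison in item 22a is "Change in the overall KCCQ scores from baseline to five months, by study arm".

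Three places bring in a propensity score or baseline covariates:

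- Item 16b, adjusted ITT. Purpose: "To adjust for early withdrawals, a propensity score for receiving the intervention will be developed". Method: "The adjusted ITT analysis will be performed adjusting for the propensity score and for baseline covariates that were different between arms".
- Item 25a, robustness analyses: "Additional analyses will be done to check robustness if the two arms differ at baseline by controlling for the propensity score". The sentence goes on to allow the covariates behind the score instead, so that the choice is "controlling for the propensity score or the covariates that were important in the propensity score".
- Item 23a, also conditional on baseline differences: a "propensity scores approach will be used to obtain the desired marginal effect estimates under the counterfactual assumption of balanced arm".

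None of the three mentions a covariate-by-visit term. The robustness sentence names no base model, and item 23a names no propensity method. Item 25a also gives an alternative analysis of covariance (ANCOVA) in which follow-up "outcome measures will be regressed on the corresponding baseline outcome measures and study arm". Aim 2 reuses the Aim 1 mixed models.

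**The concern.** Adjusting or controlling for a variable ordinarily means adding it to the regression. The ITT regression is the arm-by-visit mixed model. In that model a time-constant covariate with a single coefficient describes only the participant's overall level. It cannot represent a factor that makes scores rise or fall over follow-up, and that is the kind of factor that would confound a difference in change.

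Early withdrawal was 27/106 = 25.5% in the intervention arm and 4/86 = 4.7% in the control arm (item 19). The ITT set requires at least one follow-up visit, so most or all of these participants leave the analysis. Item 16b is the analysis said to deal with this. Little else does. Item 25c gives no sensitivity analyses, the ANCOVA as written contains only baseline outcome and arm, and the weighted imputation in item 24b is described for incomplete questions and forms. If the adjusted analysis is nearly bound to match the primary one, the match would be reported as robustness although it carries almost no information.

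**Working it through.** **1. The plan's own figure.** Section 3, item 7 uses SD 20, difference 10, two-sided alpha 0.05 and 80% power. n per arm = 2 × (1.960 + 0.842)² × 20² / 10² = 62.8, so 63. With 80% retention, 63 / 0.8 = 78.75, so 79. Both agree with the plan. The 10-point difference and SD of 20 set the scale below.

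**2. Algebra, complete data.** Let dY_t be the raw arm difference in mean KCCQ at visit t, dx the arm difference in the mean of a baseline covariate or score, and g its single coefficient. The adjusted arm difference at visit t is

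D_t = dY_t − g·dx.

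The effect is D_5 − D_0 = (dY_5 − g·dx) − (dY_0 − g·dx) = dY_5 − dY_0. The covariate drops out whatever g and dx are, and under any within-person covariance. With a visit-specific coefficient g_t the effect becomes (dY_5 − dY_0) − (g_5 − g_0)·dx, which does remove confounding of change.

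**3. Simulation at the trial's retention.** From item 20: 79 and 82 participants, 75 and 78 at month 1, 60 and 59 at month 5. Assumed, not in the documents: true effect 0; covariate imbalance 0.5 SD; covariate worth 8 points per SD on level and either 0 or 6 points per SD on month-5 change; random-intercept and residual SD 14 each (SD of change √2 × 14 = 19.8); nested dropout; 40 data sets per scenario.

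Shift in the month-5 estimate when the covariate or score is added as a main effect:

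- Complete data: 0.000000 in every data set, standard error unchanged.
- Dropout completely at random: mean absolute shift 0.12 to 0.17, maximum 0.58; standard error about 3.5.
- Dropout depending on the covariate, same direction in both arms: 0.14 to 0.20, maximum 0.60.
- Dropout depending on the covariate, opposite directions by arm (an extreme case): mean shift −1.0 to −1.3, largest 1.9.

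The month-1 estimate did not move under nested dropout.

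Mean month-5 estimate when the covariate predicts change by 6 points per SD (expected bias 0.5 × 6 = 3.0):

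| Analysis | Random dropout | Same direction | Opposite by arm |
|---|---|---|---|
| Mixed model, unadjusted | 2.58 | 2.34 | 6.77 |
| + score, main effect | 2.57 | 2.42 | 5.44 |
| + score × visit | −0.62 | −0.71 | −1.15 |
| ANCOVA, baseline and arm | 4.03 | 3.91 | 9.79 |
| ANCOVA + score | −0.20 | −0.19 | −0.79 |
| Score as weights, change | −0.71 | −0.66 | 3.08 |

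The simulation error of each mean is about 3.5/√40 = 0.55, so values within about 1.1 of zero are compatible with no bias.

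**4. Other assumptions.** In 300 trials with imbalance 0.4 SD and a covariate worth 4 points per SD at baseline and 10 at month 5 (expected bias 0.4 × 6 = 2.4), the bias was 2.44 unadjusted, 2.45 with the score as a main effect and 0.11 with score × visit. The mean absolute gap between unadjusted and main-effect estimates was 0.15. A further run at the stated retention gave an average shift of about 0.17, maximum 0.88.

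**5. Where cancellation is correct.** If the covariate affects level only (0 points per SD on change), the unadjusted mean was −0.44 under same-direction dropout, within simulation error of zero. The change contrast is then already free of that imbalance.

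**The case against.** The plan never states the model criticised here. The robustness sentence comes straight after the ANCOVA paragraph, and in an ANCOVA the score acts as intended: it moved the estimate by about 4.2 points in the random-dropout column. Item 23a speaks of marginal effects, which suits weighting or standardisation at least as well as a regression term. Item 16b does not rule out a visit interaction. The trial is also described as a pilot, these analyses are supportive, and the planned ANCOVA already handles imbalance in baseline KCCQ itself.

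All of this stands, and it limits the point to the most direct reading of item 16b with item 25a. It does not dispose of it: an analyst following those two items literally would fit the nearly uninformative model, and nothing in the plan prevents that.

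A reader might also infer three stronger things that the documents do not support:

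- That the adjusted analyses must reproduce the primary result by construction. This is exact only with complete data, and month-5 retention was 75.9% and 71.9%.
- That the primary KCCQ result is biased by 2 to 3 points. That size comes from the assumed imbalance and covariate effects, is smaller than the standard error of about 3.5, and is zero if no imbalanced factor predicts change.
- That every outcome is affected. The hospital and emergency counts in item 22b are follow-up counts adjusted for the prior three months, and in a model of that form a covariate main effect can move the arm estimate.

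**Conclusion.** The concern holds for KCCQ and the Aim 2 change outcomes under the most direct reading of items 16b and 25a. A main-effect-only score or covariate leaves the difference in change untouched with complete data. At the stated retention it usually moves it by well under 1 point, and by up to 1.9 only under strongly arm-differential dropout. The cancellation is algebraic and needs no assumption beyond the model form. The simulated bias does rest on assumptions: it is roughly the imbalance times the covariate's effect on change, which gave 0 to 3.0 points over the non-differential settings tried.

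Agreement between the primary and adjusted results would thus be weak evidence that the 27/106 versus 4/86 withdrawals did no harm. This should be fixed, but it is not critical: the primary estimate, its population and its test are unchanged.

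**What to change.** In items 16b and 25a, and for Aim 2, state one of the following:

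- the propensity score and each baseline covariate enter the mixed model together with their interactions with visit; or
- they enter the month-1 and month-5 ANCOVA alongside the baseline outcome; or
- the score is used as weights, with the weight formula given.

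In item 23a, name the propensity method that yields the marginal effect. State that a mixed model with the score or covariates as main effects only will not be reported as a robustness check. If weights are chosen, say how later loss to follow-up is handled, since weighting left 3.08 points of bias in the opposite-dropout scenario.

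The cost is a sentence or two in the plan and, with three visits, two extra coefficients per covariate. In the random-dropout scenario the standard error rose from 3.535 to 3.551; in the opposite-dropout scenario it rose from about 3.52 to 4.05. Any of these options addresses measured factors only.

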2. Patients with six or more hospital admissions within the last twelve months
3. Patients who are being discharged to a living facility that provides meals to residents.

4. Patients who anticipate moving from their current housing situation to one that does not meet our inclusion criteria within six months of enrollment.
5. Patients who are part of meal provision program that provides more than 7 meals a week to the patient.
6. Patients who are unable to feed themselves and do not have adequate support to help them with feeding.
7. Patients with limited physical, cognitive, or behavioral abilities that would interfere with their ability to follow-up with a study as determined by their ability to receive the Project Open Hand services and follow up with survey interviews
8. Patients with anticipated life expectancy of less than a year.
9. Patients who lack capacity to consent to a research study.
10. Patients currently requiring dialysis or determined to need dialysis in the next 6 months.
11. Patients with severe allergies to eggs, soy, wheat, nuts, seeds, seed oils, pineapple, raisins, or certain vegetables such as onions (allergies are considered on a case-by-case basis in consultation with Project Open Hand).

19) **Recruitment** – A CONSORT flow diagram will be used to summarize the number of participants who were:

- a. Assessed for eligibility at screening
 - i. Among people with heart failure, 2996 people were assessed for eligibility
 1. 2451 did not meet the inclusion criteria
 2. 127 Discharged before doing the baseline evaluations
 3. 226 were not interested in participating in the study
 - ii. Eligible and randomized
 1. 192 were eligible and randomized
 - a. 106 allocated in the intervention arm
 - i. 27 were early withdrawals
 - b. 86 allocated in the control arm
 - i. 4 were early withdrawals

See CONSORT diagram for detail on reasons for ineligibility

20) Withdrawal/follow-up

Reasons and details of withdrawal and lost to follow up at month 1 and 5 for both arms will be reported and summarized in the CONSORT flow diagram.

- a. Level of withdrawal, e.g., from intervention and/or from follow-up
 - i. Participants were withdrawn from the study due to unavailability to immediately reach out by phone, not meeting the eligibility criteria or deceased immediately following the randomization.

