- i. Hospitalization and Emergency Department use: As a secondary Aim 1 outcome, self-reported data as well as abstracted medical record data on hospital readmission and Emergency Department use were collected. From the data we will assess the number of times participants were admitted to the hospital from baseline to 1 month and from baseline to five months and the cumulative probability of being hospitalized by study arm. The following outcomes will be reported:

1. Admissions to Zuckerberg San Francisco General Hospital from baseline to 1 month, as determined by medical records. Number of admissions to Zuckerberg San Francisco General Hospital from baseline to 1 month, by study arm, adjusting for baseline values (-3 to 0 months).
2. Admissions to Zuckerberg San Francisco General Hospital from baseline to 5 months, as determined by medical records. Number of admissions to Zuckerberg San Francisco General Hospital from baseline to 5 months, by study arm, adjusting for baseline values (-3 to 0 months).
3. Admissions to any hospital from baseline to 1 month, as determined by ZSFGH medical records and self-report of admission to hospitals other than ZSFGH. Number of admissions to any hospital from baseline to 1 month, by study arm, adjusting for baseline values (-3 to 0 months).
4. Admissions to any hospital from baseline to 5 month, as determined by ZSFGH medical records and self-report of admission to hospitals other

than ZSFGH. Number of admissions to any hospital from baseline to 5 months, by study arm, adjusting for baseline values (-3 to 0 months).

- a. Cumulative probability to be admitted to any hospital from baseline to 5 months by study arm.
- 5. Emergency room utilization at Zuckerberg San Francisco General Hospital from baseline to 1 month, as determined by medical records. Number of admissions to the emergency room at Zuckerberg San Francisco General Hospital from baseline to 1 month, by study arm, adjusting for baseline values (-3 to 0 months).
- 6. Emergency room utilization at Zuckerberg San Francisco General Hospital from baseline to 5 months, as determined by medical records. Number of admissions to the emergency room at Zuckerberg San Francisco General Hospital from baseline to 5 months, by study arm, adjusting for baseline values (-3 to 0 months).

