- 7. Emergency room utilization at any hospital from baseline to 1 month, as determined by ZSFGH medical records and self-report of emergency room utilization at hospitals other than ZSFGH. Number of admissions to any emergency room from baseline to 1 month, by study arm, adjusting for baseline values (-3 to 0 months).
- 8. Emergency room utilization at any hospital from baseline to 5 month, as determined by ZSFGH medical records and self-report of emergency room utilization at hospitals other than ZSFGH. Number of admissions to any emergency room from baseline to 5 months, by study arm, adjusting for baseline values (-3 to 0 months).

ii. Overall health-related quality of life. Self-reported quality of life using the 4-item Healthy Days Core Module of the CDC's Health-Related Quality of Life survey which asks a general assessment of health on a 5-point Likert scale as well as 3 questions quantifying the number of days in the past 30 days participants felt their health was not good.

c. Aim 2 Outcomes. The primary intermediate outcomes are changes between baseline, 1 month and 5 months in food security, diet quality, depressive symptoms, and medication adherence.

- i. Food Security: We measured food security status using the 10-item adult version of the USDA Household Food Security Survey Module (HFSSM) Access Scale (HFIAS). This scale has been validated in Spanish and English in the US and is the reference measure for food security in the US [citations]. The ten-item questionnaire covers domains of worry over, sufficiency of, and quality of food accessed by the participant's household. The scores will be analyzed primarily as a continuous variable using a sum of all responses with a possible range of 0 to 18 in households with children, and 0 to 10 in households without children. Higher scores are indicative of less food security. We will examine the following outcomes:
 - 1. Change in food security scores from baseline to 5 months, by study arm.
 - 2. Change in food security scores from baseline to 1 month, by study arm.

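### The conditional Box-Cox rule for skewed secondary outcomes cannot be applied to admission, ED-visit and unhealthy-day counts that include zeros, and the plan names no count analysis in its place

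*Combined protocol and SAP*

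**What the plan says.** Section 6, item 25, part a sets the main model for Aim 1: "Intent-to-treat analyses will assess whether the intervention will result in improved changes in primary and secondary outcomes with mixed effects models". The fixed effects are arm, visit and their interaction, with individuals as random effects. No distribution or link is named. A second approach follows: "Alternative analyses will be done using analysis of covariance". For skewed data the rule is: "For primary and secondary outcomes, Box-Cox transformations will be used to correct for skewness if needed". No added constant, rule for choosing the power, or treatment of zeros is given. Sensitivity analyses are marked as not applicable.

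Item 22, part b defines the secondary outcomes. Part b.i lists eight utilisation counts: admissions and ED visits, at the study hospital and at any hospital, to 1 month and to 5 months. Each is to be adjusted for the count in the 3 months before baseline. The first reads "Number of admissions to Zuckerberg San Francisco General Hospital from baseline to 1 month, by study arm". Part b.ii adds the Healthy Days module, with one 5-level item and "3 questions quantifying the number of days in the past 30 days participants felt their health was not good".

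One utilisation analysis lies outside this rule: "To compare the probabilities of hospitalization and emergency room visits by study arm, a log-rank test will be performed", shown with Kaplan-Meier curves.

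**The concern.** Box-Cox with an estimated power needs strictly positive data, and standard software refuses a variable that contains a zero. Patients with no readmission, no ED visit or no unhealthy day score zero. Counts of this kind are also the outcomes most likely to be skewed, so the condition in the rule is likely to be met where the rule cannot be carried out.

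The analyst would then have to choose a constant. No power transformation removes a spike at zero, so the result can depend on that choice. The estimate also changes meaning. Item 22 promises numbers of admissions by arm, but a difference in shifted, power-transformed counts cannot be read as admissions avoided. It also gives less weight to repeat admissions, which are part of what the outcome is meant to capture.

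**Working it through.** **The plan's own figure.** The only sample size is for the KCCQ: 2 × (1.96 + 0.8416)² × 20² / 10² = 62.8, so 63 per arm; 63 / 0.80 = 78.75, so 79 per arm and 158 in total. It reproduces and is not affected. The plan has no figure for the counts.

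**Will there be zeros?** Item 18 excludes "Patients with six or more hospital admissions within the last twelve months", so patients enter with at most 5 admissions a year. If that prior rate r continued (an assumption), the Poisson zero share over t months is exp(−r·t/12):

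| Admissions per year | Zeros at 1 month | Zeros at 5 months |
|---|---|---|
| 5 (the cap) | exp(−5/12) = 66% | exp(−25/12) = 12% |
| 2 | 85% | 43% |
| 1 | 92% | 66% |

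Zeros are close to certain even at the cap. For unhealthy days the share of zeros is unknown.

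**How much could it matter?** Event rates are assumed. Counts are negative binomial with variance m + m² (dispersion 1), in 79 vs 82 patients, the numbers left after early withdrawals in item 20. The zero share is 1/(1+m): 45% at mean 1.2 and 56% at 0.8. Three tests are compared: a log rate ratio with robust variance, an untransformed t-test, and a t-test after maximum-likelihood Box-Cox of count + c. There are 2,000 simulated trials per row (Monte Carlo error about 1 point). Entries are % of trials with p<0.05; the last two columns are % of trials in which the verdict differs from the rate-ratio test.

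| Means, control vs intervention | Rate ratio | Raw t | Box-Cox, c=1 | Box-Cox, c=0.01 | Differs, c=1 | Differs, c=0.01 |
|---|---|---|---|---|---|---|
| 1.2 vs 0.8 (5 months) | 46.2 | 44.4 | 36.8 | 32.6 | 18.6 | 23.2 |
| 0.8 vs 0.5 (5 months) | 46.0 | 43.6 | 35.2 | 32.8 | 20.8 | 23.1 |
| 1.2 vs 0.7 (5 months) | 64.5 | 62.7 | 53.3 | 47.0 | 19.5 | 25.3 |
| 1.5 vs 0.9 (5 months) | 65.4 | 63.2 | 54.1 | 47.8 | 18.4 | 25.4 |
| 0.3 vs 0.2 (1 month) | 20.6 | 19.6 | 17.6 | 17.7 | 10.5 | 10.8 |
| 1.2 vs 1.2 (no effect) | 6.2 | 5.7 | 5.8 | 5.7 | 4.8 | 6.2 |

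The 5-month loss runs from 46.2 − 36.8 = 9.4 to 65.4 − 47.8 = 17.6 points. Across repeated runs with the same assumptions the range was about 8 to 20 points, with the verdict changed in about 17% to 27% of trials. Changing only the constant, from 1 to 0.01, altered the verdict in 3% to 8% of these 5-month trials.

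**Other dispersions.** With dispersion 0.3 (1.2 vs 0.7), power at c=1 falls only from 82% to 78%. With dispersion 0.05 (1.2 vs 0.8) it falls from 68% to 64%. With dispersion 2, control mean 0.9 and rate ratio 0.5, it falls from 64% to between 38% and 43% over constants from 0.001 to 1.

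**Unhealthy days** (assumed 0–30 counts with extra mass at 0 and 30; 60 vs 59 patients, the numbers retained at 5 months; log(y + c) in place of a fitted Box-Cox). For an effect on severity only, power fell from 38% untransformed to 8–22%. For an effect on the share of zeros only, it rose from 10% to 23–33%.

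**The case against.** The rule is conditional, and item 24 says the analyst will inspect outcome distributions. A careful analyst might never apply Box-Cox to these counts. The added constant is an inference about how the rule would be carried out, and the plan does not say that its mixed models are linear. These points stand in part. The ANCOVA alternative and the Box-Cox rule make a linear model the natural reading, though, and no other route for skewed counts is written down.

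The simulation is a plain two-group comparison. It has no repeated measures and no adjustment for the pre-baseline count, and its rates are assumed. It shows the possible size, not this trial's loss. The untransformed t-test also comes within about 3 points of the rate ratio, so most of the power returns once Box-Cox is dropped. The case for a count model rests more on the estimate it gives than on power.

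A reader might infer three stronger things.

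- **That the whole utilisation result hangs on an arbitrary constant.** It does not. The log-rank test and the cumulative probability of admission do not use Box-Cox, and raw counts by arm could still be tabulated. Utilisation is also secondary in a pilot trial.
- **That power is always lost.** It is not: the loss is about 3 points or less in the 1-month row, and some unhealthy-day effects gain.
- **That the direction of effect would reverse.** This requires crossing distributions. With means of 0.78 (control) and 0.62 (intervention) and zeros of 60% and 55%, the log(y + c) difference is +0.24 at c=0.001 and −0.03 at c=1, neither near significance. If one arm is stochastically lower throughout, a monotone transformation cannot reverse the true direction. Nothing in the documents points to crossing.

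**Conclusion.** The point holds in limited form. The stated skewness rule covers outcomes on which it cannot run, and the plan supplies neither a constant nor a count analysis. That rests on the text and the near-certainty of zeros, not on simulation. It is also certain that a shifted, transformed difference is not the quantity item 22 promises.

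The size rests on assumed rates. At dispersion 1 it is about 8 to 20 points of power for 5-month counts; it is less with weaker overdispersion, up to about 26 points (64% to 38%) with stronger, and small at 1 month. Type I error stays near 5%, so this is not a false-positive problem. The KCCQ sample size and the log-rank analysis are untouched, but the log-rank test addresses occurrence and timing and cannot replace the eight count comparisons. The change should be made, but it does not threaten the primary analysis.

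**What to change.** - Limit the Box-Cox sentence in item 25, part a to strictly positive continuous outcomes.
- Analyse admission and ED counts untransformed with one prespecified count model, for example negative binomial regression with robust variance. Use log follow-up time as offset, because of deaths and losses, and the count from the 3 months before baseline as covariate. Report the rate ratio and the rate difference with 95% confidence intervals.
- Analyse the three unhealthy-day items on the day scale with robust or bootstrap standard errors. The 5-level health item has no zero problem and needs no change on this account.
- Keep the log-rank and Kaplan-Meier analysis as it is.

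The cost is one SAP paragraph and no new data, and these are standard regression models. Rate ratios need slightly more explanation than mean changes; the rate difference helps with that.
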